## **iib-8. Outcomes and their measurements**

### **Primary Outcome: *Patient-Reported Satisfaction and Quality of Life***

Patient satisfaction and quality of life will be measured using the Breast Q $\circ$  as a self-administered questionnaire. The Breast Q $\circ$  has 2 subscales that examine the two different domains: satisfaction and psychosocial function. The scores generated for each subscale will be transformed on a scale from 0-100, lowest to highest summary scores respectively. Scale validity and reliability are supported by the high Cronbach's alpha coefficient (>0.80) and intra-class correlation coefficients (>0.70). The scores generated for each subscale will be transformed on a scale from 0-100, lowest to highest summary scores respectively. Participants will be asked to complete the pre-operative module of the Breast Q $\circ$  questionnaire at 2 weeks prior to the mastectomy.(APPENDIX 4) Post-operatively, they will be requested to complete the post-operative module of the Breast Q $\circ$  at 2 weeks following immediate reconstruction, as well as 6 months and 1 year following the completion of the reconstruction. (APPENDIX 5) The questionnaires will be self-administered and mailed to the participants with return envelopes and prepaid postage. To compensate our study patients for their participation, a monetary reimbursement (\$10) will be available upon completion. The Dillman method will be used to encourage patient response.

The **secondary outcomes** will include a comparison of:

1. **short and long-term complication rates**: Short-term complications are intra- and post-operative complications occurring within two months of surgery and long-term complications occur later than two-months. They will be documented and collected prospectively.
2. **long-term aesthetic result**: Evaluation of the overall aesthetic result and capsular contracture grade will be performed at six months and one year following the completion of reconstruction. A routine physical examination will be performed by the attending surgeon and photographic documentation (5 standardized photographs) of the reconstruction will be obtained at the six month and one-year follow-up visit. A panel of three independent, blinded observers will subsequently evaluate the overall aesthetic result using the three-point, five item, Breast Aesthetic Score described by Lowery with the use of photographic documentation. Capsular contracture will be graded by the examining physician and will be graded using the Modified Baker Scale for Reconstructed Breasts, which is widely accepted to be the gold-standard measure of capsular contracture grade.
3. **cost-effectiveness**: Costs and effects will be simultaneously analyzed by collecting person-level cost and effect data. The cost data will come from hospital cost accounting systems and patient reports. The patient outcome data will be collected at months 6 and 12 months post-mastectomy by Breast Q $\circ$

and EQ-5D. The frequently used generic HRQoL instrument EQ-5D will be piggy-backed to the Breast QoL at the 2 post-mastectomy time-points to generate a utility value for current health. The primary measure of effectiveness will be the Breast Q score and the secondary measure will be quality adjusted life years (QALY) as measured by the EQ-5D (APPENDIX 6)

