#### Study Schema:

Baseline Measure	Skin-sparing or Nipple-sparing mastectomy	Outcome Measure
Stratify by:		
1. Site	Acellular dermal matrix assisted one-stage implant reconstruction	1. Breast Q ©
UHN WCH VGH		2. EQ-5D
2. Laterality		3. Complications
Unilateral Bilateral		4. Aesthetics
	Two-stage tissue expander/implant reconstruction	5. Cost-effectiveness

The **primary outcome** evaluated will be **patient-reported satisfaction and quality of life** associated with the use of ADM in one-stage immediate prosthetic breast reconstruction following skin-sparing or nipple-sparing mastectomy. Patient-reported satisfaction and quality of life will be measured using the Breast Q© questionnaire. These questionnaires will be administered to patients prior to mastectomy, at two weeks following the mastectomy and immediate reconstruction, 6 months and one year (+/- 1 month) following completion of reconstruction. It is hypothesized that ADM assisted one-stage prosthetic breast reconstruction will be associated with improvement in patient-reported satisfaction and quality of life compared to the conventional two-stage TE/implant reconstruction.

The **secondary outcomes** will include **short and long-term complication rates**, overall **aesthetic outcome** including capsular contracture formation at six month and one-year following completion of the reconstruction, and a **cost effectiveness analysis (CEA)**. For the cost-effectiveness analysis, person-level cost and effect data will be collected throughout the study. The cost data will come from hospital cost accounting systems and patient reports. The patient outcome data will be collected at months 6 and 12 months post-mastectomy by the Breast Q© and EQ-5D. The primary measure of effectiveness will be the global Breast Q© score and the secondary measure will be quality adjusted life years (QALY) as measured by the EQ-5D. It is hypothesized that the short- and long-term complication rates will be comparable between the two study arms, while the overall aesthetic outcome will be superior with less severe capsular contracture in the ADM assisted one-stage than the two-stage TE/implant reconstruction. Lastly, we hypothesize ADM assisted one-stage implant reconstruction will be the more cost effectiveness method of implant reconstruction following mastectomy than the standard two-stage TE/I method.

Timing of Questionnaires

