#### Subject Exclusion Criteria

- Patient refusal
- Patients with documented psychiatric history of psychosis or mental disorder excluding depression
- Patients who are active smokers
- Patients who will undergo any of the following:
  - Autologous tissue reconstruction
  - Combined implant and autologous tissue reconstruction
  - Patients with prior history of radiation or expected to receive post-operative radiation
  - Patients who are pregnant
  - Patients with grade III ptosis
  - Patients desiring final breast volume of greater than C cup

Following randomization preoperatively, eligibility will be determined once more intraoperatively:

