#### iib-4. Intervention plan

##### ***Pre-intervention Evaluation***

During the pre-operative consultation, written informed consent will be obtained from patients who meet the inclusion and exclusion criteria and who are willing to participate. (APPENDIX 3)

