##### ***Randomization***

Randomization will occur in during the pre-operative consult although the participant's final eligibility will be determined during surgery (see section on Eligibility). Patients will be randomized to undergo either ADM assisted one-stage reconstruction or two-stage reconstruction with TE placement without the use of ADM. The randomization allocation list will be developed by the Department of Epidemiology and Biostatistics at the University Health Network Research Institute. Sequentially numbered and sealed envelopes containing the treatment assignments will be prepared and given to the study coordinator in charge of the study site. Each envelope will contain two identical datasheets with the patient's name, medical record number and treatment assignment. One sheet will be returned to the study coordinator and the other sheet will be placed in the patient's chart.

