### **9c. Measurement of the Primary Objective:**

#### ***i) Primary Analysis***

Each of the two domain-specific summary scores on function and satisfaction will be transformed on a scale from 0 to 100 using RUMM software. Mean scores and standard deviation for each surgery group will be calculated and compared. To address our primary aim of comparing patient satisfaction and quality of life between **Group 1** (one-stage with ADM) and **Group 2** (two-stage group without ADM) before and at the three post mastectomy follow up reference time points, we will use the **repeated measure analysis** to examine the time effect and time-group interaction. In all analyses, statistical significance will be designated at  $p <= 0.05$  level.

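### The baseline Breast Q probably follows allocation for most women, and nothing requires it to come first, so knowing the arm could shift the score that enters the time-by-group interaction

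*Combined protocol and SAP*

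**What the plan says.** The steps are spread over several sections of the combined protocol and SAP.

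- **Consent** (iib-4, Pre-intervention Evaluation): "During the pre-operative consultation, written informed consent will be obtained from patients who meet" the entry criteria.
- **Allocation** (iib-4, Randomization): "Randomization will occur in during the pre-operative consult". Sealed envelopes are held by the site coordinator. Each contains two assignment sheets: one goes back to the coordinator and "the other sheet will be placed in the patient's chart". The section does not say when the envelope is opened or when the woman is told.
- **Order relative to surgery** (iib-3): "Following randomization preoperatively, eligibility will be determined once more intraoperatively".
- **Baseline Breast Q** (iib-8, Primary Outcome): the pre-operative module is a "questionnaire at 2 weeks prior to the mastectomy". The text under the Study Schema in iib-1 is looser: "These questionnaires will be administered to patients prior to mastectomy".
- **Mode** (iib-8): "The questionnaires will be self-administered and mailed to the participants with return envelopes and prepaid postage". This sentence follows the description of both the pre-operative and post-operative modules and exempts neither.
- **Use in the analysis** (9c, Primary Analysis): the groups are compared "before and at the three post mastectomy follow up reference time points", by a repeated-measures analysis that examines the time effect and the time-by-group interaction.

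The only blinding described anywhere is that of the three-member photograph panel (iib-8).

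**The concern.** A baseline serves as a pre-treatment reference only if allocation cannot have influenced it. Here the baseline is timed from surgery, whereas allocation is tied to the consult, and no rule puts one before the other.

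The instrument is a self-report of satisfaction and psychosocial function. The arms differ visibly in the number of operations, the expansion visits and the use of donor dermis. A woman who knows which she will have may answer differently from one who does not.

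A difference between arms that arises in this way comes after randomization, so randomization does not balance it. Adjustment for the covariates listed in iib-7 and 9a does not remove it either. Because the baseline is one of the repeated measures, a shift confined to it makes the group difference vary over time. The interaction test would read that as an effect.

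**Working it through.** **Order of events.** Suppose consent and randomization happen at one visit, as iib-4 describes. A form mailed to a consented participant then reaches her after that visit, and so after allocation, whatever the interval to surgery. The baseline precedes allocation only if randomization is deferred to a later date, or if the form is handed out and completed at the consult before the envelope is opened. The plan provides for neither. Deferral may still occur: Preliminary Data (iia-3) reports 67 women registered, 51 randomized and 16 awaiting randomization.

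**The plan's own figure.** Sample Size (iib-10) gives a difference of 10, SD 20, alpha 0.05 and power 85%. Taking the test as two-sided:

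n per arm = 2 × 20² × (1.960 + 1.036)² / 10² ≈ 71.8, rounded up to 72. This matches, and power at 72 per arm is 0.851. The calculation is a two-group comparison that does not use baseline. This point does not change N.

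**Form of the bias.** Let b be the between-arm shift at baseline caused by knowing the arm, k the fraction of it still present at follow-up, and δ the true follow-up difference apart from that shift.

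- Change-from-baseline contrast: (δ + kb) − b = δ − (1 − k)b. The bias is b in size if k = 0 and smaller if part of the shift persists.
- Baseline as a covariate, with baseline/follow-up correlation r and k = 0: the bias is about r × b.
- Post-operative scores without baseline: the baseline score is not used, so its timing has no effect.

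**Illustration.** b (2 or 4 points), r (0.3 to 0.7) and k = 0 are assumptions that the documents do not supply. SD 20 and 72 per arm come from iib-10. The standard errors are

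- change: 20 × √(2(1 − r)) × √(2/72), which is 3.33 at r = 0.5;
- covariate: 20 × √(1 − r²) × √(2/72), which is 2.89 at r = 0.5.

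Two-sided type I error with no true effect (nominal 0.05):

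| b | Change: r = 0.3 / 0.5 / 0.7 | Covariate: r = 0.3 / 0.5 / 0.7 |
|---|---|---|
| 2 | 0.080 / 0.092 / 0.121 | 0.054 / 0.064 / 0.090 |
| 4 | 0.174 / 0.224 / 0.341 | 0.066 / 0.107 / 0.217 |

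Power for a true 10-point difference at r = 0.5, if the shift runs against it:

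| b | Change | Covariate |
|---|---|---|
| 0 | 0.851 | 0.934 |
| 2 | 0.670 | 0.877 |
| 4 | 0.436 | 0.791 |

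These figures describe a single follow-up-minus-baseline contrast. The planned interaction covers four time points and is a joint test, so they show the mechanism and its scale. They do not predict the operating characteristics of the planned test.

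**The case against.** The other side has real points, and most of them limit the claim.

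- **The order is inferred.** A reader might conclude that every baseline is a post-randomization measurement. The documents do not say so. The consult-to-surgery interval is not given, and the 16 registered women not yet randomized show that the steps were not always simultaneous. This stands: the order is probable for most women but not established for all.
- **Disclosure is inferred.** A reader might conclude that women learn their arm at the consult. The Randomization section does not say this. It remains likely that a woman preparing for one operation or for two knows which before surgery, and nothing keeps it from her.
- **The recorded worries come from other women.** Section iia-2 lists reluctance about randomization and concern about ADM as reasons for refusal, given by the 11 who declined out of 78 approached. It is tempting to use these as evidence that enrolled women's scores would move. They are not, because those women did not enter the trial.
- **The size is assumed.** Nothing in the documents supports a shift of 2 to 4 points, or a direction. The pre-operative module is in an appendix that is not part of the text, so how far its items respond to a known assignment cannot be judged here.
- **Full bias is the extreme case.** It applies to a change contrast when none of the shift persists. The objectives (section i) state the hypothesis as higher scores at the three follow-up times, and 9c also compares group means. Those comparisons do not depend on the baseline.

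What the objections leave in place is that the schedule, followed as written, puts an unblinded self-report baseline after allocation, and that the named primary method uses it.

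**Conclusion.** The concern holds as a risk created by the stated schedule. Baseline will probably follow allocation for most women, and the plan gives no way to tell which baselines came before it. If knowing the arm moves the score by b points, a change-from-baseline contrast is biased by at most b (when the shift does not last to follow-up), and a baseline-adjusted contrast by about r × b. The size and sign of b are unknown, so the calculated error rates are conditional illustrations.

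The documents do not show that bias has occurred or that the trial's primary comparison is invalid. Post-operative group comparisons, including the one on which the sample size rests, are untouched by this problem. It is worth correcting because the correction is cheap and the exposure falls on the analysis named as primary.

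**What to change.** - **Protocol text.** Amend the Randomization part of iib-4 and the Primary Outcome part of iib-8 so that the pre-operative Breast Q is completed after consent and before the allocation envelope is opened. Apply the same rule to the baseline EQ-5D in the Timing of Questionnaires table (iib-1). Record the date of completion and the date of allocation for every woman.
- **Women already randomized.** Report for each whether baseline preceded allocation. Add a sensitivity analysis that compares post-operative scores without baseline. Analyse the subset with a pre-allocation baseline only if enough women qualify, since it may be nearly empty or a selected group.
- **Who benefits.** On the Preliminary Data figures, 144 − 51 = 93 women (65%) were still to be randomized. The number at the time of any amendment may be smaller.
- **Cost.** Some minutes of clinic time, a longer gap between baseline and surgery, and a clinic-versus-mail difference in mode between baseline and follow-up. The mode difference is the same in both arms. The sample size does not change.

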1. To compare patient satisfaction and QOL between one-stage ADM and two-stage TE/I reconstruction without ADM following mastectomy. Patient satisfaction will be evaluated using the Breast Q© at two-weeks, as well as six months and one year following completion of reconstruction.

**Hypothesis:** Patient satisfaction and QOL will be higher in the ADM assisted one-stage implant reconstruction group compared to the two-stage TE/I group at all three time-points.

The **secondary objectives** of this study are:

1. To compare the short- and long-term complication rates between the two techniques.

**Hypothesis:** The use of ADM in one-stage prosthetic breast reconstruction is not associated with increased short- and long-term postoperative complications compared with the traditional two staged TE/I procedure.

2. To examine the overall aesthetic outcome achieved using the ADM facilitated one-staged breast reconstruction at six months and one year following completion of the reconstruction.

**Hypothesis:** The overall aesthetic outcome achieved using the ADM facilitated one-stage breast reconstruction is superior to that following the two-stage breast reconstruction.

3. To perform a cost-effectiveness analysis (CEA) of the two reconstruction methods using the net benefit regression model on person-level cost and effect data collected during the study.

**Hypothesis:** Both the direct and indirect cost will be reduced and patient-reported utility will be greater for the one-stage ADM method compared to the TE/I method.

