### ***Group A: Experimental Treatment***

In **Group A**, the experimental group, the plastic surgeon will create the breast pocket which will involve the use of an implantable layer of ADM. Pocket dissection will begin with elevation of the pectoralis major muscle. ADM will be used to create the infero-medial pocket thereby eliminating the need for surgical elevation of the anterior rectus fascia as well as the serratus musculature/fascia. It will be secured to the lateral border of the pectoralis major using absorbable sutures. Inferiorly, it will be sutured to the anterior rectus fascia along the base of the implant pocket. Laterally, it will be sutured to the serratus fascia in the line of the anterior axillary fold. A permanent anatomic cohesive silicone gel (Style 410, Allergan, Santa Barbara, CA) will be placed in the pocket and complete closure of the pocket will be performed using an absorbable suture. Two drains will be placed in the breast pocket, one deep to ADM and one on the superficial surface of ADM at the inferior mastectomy gutter.

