### ***Group B: Standard Treatment***

In **Group B**, the standard treatment group, the tissue expander pocket will be made by elevating the pectoralis major muscle, serratus anterior muscle/fascia laterally and rectus fascia inferiorly. An anatomic-shaped tissue expander (Allergan, Santa Barbara, CA) will be placed beneath the muscle-fascial pocket and pocket will be closed using an absorbable suture. Sterile injectable saline will be used to inflate the tissue expander until an adequate volume without tension on the mastectomy skin flap is achieved. In this case, only one drain will be placed deep to the mastectomy skin flaps. All patients will receive standard peri-operative antibiotics.

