#### **iib-6. Postoperative treatment**

In **Group B**, at 2 weeks after the operation, office expansion will be undertaken and continued on a biweekly basis. With each expansion, the endpoint of expansion will include either: (1) persistent blanching or congestion of the mastectomy flap; or, (2) patient discomfort. The expansion phase will be considered complete once the volume in the expanded breast represents 100 percent (+/- 20 percent) of the recommended expander volume. If required, postoperative chemotherapy is generally given during the expansion period. Expanders are then exchanged approximately between 4-6 weeks following the completion of chemotherapy or 3-6 months following completion of inflation. All patients in group B will undergo a second exchange procedure at which time the expander is removed and a permanent implant is placed. In all instances, the permanent implant to be used will be anatomic cohesive silicone gel implants (Style 410, Allergan, Santa Barbara, CA).

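### The primary time-group interaction does not test the all-visits hypothesis and cannot tell a difference at 2 weeks, when only one arm has its permanent implant, from a lasting one

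*Combined protocol and SAP*

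**What the plan says.** Three parts of the plan bear on this.

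- **Visit timing.** Section iib-8 schedules the post-operative Breast Q "at 2 weeks following immediate reconstruction, as well as 6 months and 1 year following the completion of the reconstruction". The text under Study Schema starts from the same point: "at two weeks following the mastectomy and immediate reconstruction, 6 months and one year". The first visit is counted from the first operation in both arms, and the later two from completion.
- **State of the reconstruction at 2 weeks.** In Group A the permanent silicone implant "will be placed in the pocket and complete closure of the pocket will be performed using an absorbable suture" at the first operation. In Group B an expander goes in: "Sterile injectable saline will be used to inflate the tissue expander until an adequate volume without tension on the mastectomy skin flap is achieved". Section iib-6 then says that "at 2 weeks after the operation, office expansion will be undertaken and continued on a biweekly basis", and that "All patients in group B will undergo a second exchange procedure at which time the expander is removed and a permanent implant is placed".
- **Test and hypothesis.** Section 9c(i) takes the pre-operative score and the three follow-up scores into a repeated-measures analysis "to examine the time effect and time-group interaction", at the 0.05 level. It names no primary visit, no between-arm contrast at a visit and no direction. It also has group means and standard deviations compared, without saying at which visit. The hypothesis in section i (Specific Aims) is: "Patient satisfaction and QOL will be higher in the ADM assisted one-stage implant reconstruction group compared to the two-stage TE/I group at all three time-points".

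**The concern.** At 2 weeks the arms are rating different things: a permanent implant in one, an interim device in the other. If the later visits are timed from completion, both arms are then rating a finished reconstruction. An interaction over all four occasions responds to any departure from parallel profiles. A gap confined to 2 weeks can therefore make it significant, and so can a gap that lasts to 1 year. The test also has no direction, and it does not establish superiority at each visit, which is what the hypothesis asserts.

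At stake is the meaning of a positive primary result. The report could show a significant interaction without the plan having said whether this supports lasting satisfaction with the completed reconstruction, a better early experience, or neither.

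**Working it through.** **Inputs.** From section iib-10: 72 per arm, SD 20, relevant difference 10 points, α 0.05, power 85%. From section 9c(i): four occasions (baseline, 2 weeks, 6 months, 1 year). Assumed, because the documents give no figure: within-patient correlation ρ of 0.3 to 0.7, compound symmetry, two-sided testing, no baseline difference, and a 2-week gap of 5 to 15 points.

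**Step 1: the plan's own figure.** n per arm = 2(z₀.₉₇₅ + z₀.₈₅)² SD²/δ² = 2(1.960 + 1.036)² × 400/100 = 71.8, so 72. This reproduces. The same sentence gives a β of 0.1, which is 90% power and would need 85 per arm, so 85% is used here. The calculation is for one two-group difference, not for an interaction.

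**Step 2: the planned interaction.** With d_t the between-arm difference at occasion t, the noncentrality is λ = (n/2) × Σ(d_t − d̄)² / [SD²(1 − ρ)], on 3 and 3 × 142 = 426 degrees of freedom.

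- Early gap only, (0, 10, 0, 0): d̄ = 2.5, and Σ(d_t − d̄)² = 56.25 + 3 × 6.25 = 75.
- Sustained gap, (0, 10, 10, 10): d̄ = 7.5, and Σ(d_t − d̄)² = 56.25 + 3 × 6.25 = 75.

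Both give λ = 36 × 75 / [400(1 − ρ)] = 6.75/(1 − ρ). In each pattern one occasion stands apart from the other three by 10 points, and the test does not use which one.

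| ρ | λ, 10 points | Significant, early only | Significant, sustained | Significant, early only, 5 points |
|---|---|---|---|---|
| 0.3 | 9.6 | 74% | 74% | 22% |
| 0.5 | 13.5 | 88% | 88% | 30% |
| 0.7 | 22.5 | 99% | 99% | 49% |

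A 15-point early gap gives 98% or more throughout.

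**Step 3: simulation check** (4,000 runs, multivariate interaction test). Compound symmetry with ρ 0.5 gives 88% early only and 87% sustained. First-order autoregressive correlation of 0.6 gives 96% and 82%. The exact equality thus belongs to compound symmetry. Under the autoregressive pattern the early gap is detected more often than the lasting one.

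**Step 4: contrasts instead.** For the mean of 6 and 12 months adjusted for baseline, the residual variance is SD²[(1 + ρ)/2 − ρ²], that is 0.56, 0.50 and 0.36 times 400. The standard error is 20√(0.56 × 2/72) = 2.49, and likewise 2.36 and 2.00. A 10-point difference then has power of about 98%, 99% and over 99%. A gap at 2 weeks only would make this contrast significant at no more than the nominal 5%.

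A single visit adjusted for baseline has residual variance SD²(1 − ρ²) and power 88%, 93% and 99%. Requiring all three visits to be significant cannot have more power than that. By the Bonferroni inequality it has at least 1 − 3 × 0.118 = 65%, 1 − 3 × 0.066 = 80% and 1 − 3 × 0.013 = 96%.

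**Step 5: are the later visits after completion?** Section i, the primary-outcome paragraph under Study Schema, and section iib-8 (primary outcome) time them from completion. The cost-effectiveness text under Study Schema and in iib-8, the questionnaire timing table, 9c(i) and 9c(ii) use mastectomy or post-operative timing. As an illustration, take five inflation sessions (the average excess of clinic visits in the preliminary cost comparison), read biweekly as every two weeks, and start at week 2. Inflation then ends at about week 10. Exchange 3 to 6 months later (iib-6) falls at about weeks 23 to 36. A visit 6 months (26 weeks) after mastectomy could therefore come before exchange for some Group B women.

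**The case against.** The strongest reply is that the trial compares strategies. Avoiding expansion and a second operation is the stated rationale, 2 weeks is named as a primary visit, and a difference there under intention to treat is a real treatment effect. This stands. A reader might infer that a 2-week gap would be a false positive; the documents do not support that. Removing 2 weeks from the confirmatory analysis altogether would be a debatable choice of estimand.

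A reader might also infer that the trial could claim its primary objective from a 2-week gap alone. The hypothesis requires superiority at all three visits, so such a result would fail it as written, and the comparison of group means should make absent later differences visible. What remains is that 9c(i) contains no test or decision rule for the all-visits hypothesis.

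Nor does the interaction average the visits. A group main effect would, and the plan does not name one. With a 10-point gap at 2 weeks only, it would be significant in about 14% to 19% of trials. It would also be wrong to call the expander empty, since it is partly inflated at surgery.

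Finally, the documents give neither the size nor the sign of any 2-week gap. The schedule makes the arms' states differ; it does not establish that the scores will.

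**Conclusion.** The concern holds as a mismatch between hypothesis, test and visit schedule. The one named repeated-measures test involving treatment does not address superiority at each visit. Under compound symmetry it is equally likely to be significant for a 10-point gap at 2 weeks only as for a 10-point benefit throughout: 74% to 99% over ρ of 0.3 to 0.7. These probabilities are conditional on assumed gaps and correlations and do not predict the result. The qualitative conclusion does not depend on them: a significant interaction leaves open when the arms differ and in which direction. A 2-week difference would be genuine, but it would not be evidence about satisfaction with the completed reconstruction.

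**What to change.** In section 9c(i), replace the omnibus interaction as the confirmatory test with between-arm contrasts adjusted for the pre-operative score:

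- one contrast for the post-completion visits, as the mean of 6 and 12 months;
- a separate contrast for 2 weeks, labelled as implant in place versus expander before office expansion.

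Allow a claim of higher satisfaction with the completed reconstruction only from the first. Allow the all-visits claim only if the contrast at each of the three visits supports it, and align the hypothesis in section i with this rule. State how the 5% level is ordered or shared between the two contrasts. The interaction can stay as a description.

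Reconcile the passages that time the later visits from completion with those that time them from mastectomy or surgery; until then the post-completion label is not secure. Because the 2-week form and the first office expansion fall at the same time with no stated order, record which came first.

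The cost is wording in 9c(i), section i and the timing passages, plus one recorded item; no extra patients or visits. The trial is already accruing (67 enrolled), so the change should be dated before any Breast Q comparison by arm. The interim results reported concern complications and cost only. The downside is that an early one-stage advantage alone no longer supports the claim about the completed reconstruction, though it is still tested and reported. The all-visits claim also has less power than any single contrast.
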